8.1. Efficacy Assessments

The secondary endpoints for PsO group are:

- Proportion of participants who achieve the following PASI scores: PASI 75 (defined as 75% improvement from baseline in PASI) at Week 12
- Proportion of participants with an sPGA score of 0 or 1 (0, 1) at Week 12.

The secondary endpoints for PsA group are:

- Proportion of PsA participants achieving ACR20 at Week 24.

Exploratory endpoints include, but not limited to, DAS-28-CRP and ACR individual components.

For PsO participant who also meet active PsA definition, both PsA and PsO outcomes will be collected for that participant. Likewise, to fulfill the study objective, PsO outcomes will be collected among all the PsA participants with 3% or more BSA of PsO ([Table RHCZ.8.1](#)).

Table RHCZ.8.1. Efficacy Assessments

Assessments	PsO Participants with No Active PsA	PsA Participants with	
		≥3% BSA of PsO	<3% BSA of PsO
Clinician assessments	
 • PASI • Percentage of BSA - Psoriasis • sPGA • PGA Disease Activity VAS 	
 • TJC/SJC (68/66 joints) • PGA of Disease Activity VAS -Psoriasis • PGA of Disease Activity VAS - PsA • PASI • Percentage of BSA - Psoriasis • sPGA • DAS28 - CRP^a • ACR20/50/70^a 	
 • TJC/SJC (68/66 joints) • PGA of Disease Activity VAS - PsA • DAS28 - CRP^a • ACR20/50/70^a
Patient assessments	
 • Patient's Global Assessment of disease activity VAS - Psoriasis 	
 • HAQ-DI • PsA Pain assessment question included in HAQ-DI • Patient's Global Assessment of Disease Activity VAS - PsA • Patient's Global Assessment of Disease Activity VAS - Psoriasis 	
 • HAQ-DI • PsA Pain assessment question included in HAQ-DI • Patient's Global Assessment of Disease Activity VAS - PsA

Abbreviations: ACR20/50/70 = 20%/50%/70% improvement in American College of Rheumatology response criteria; BSA = body surface area;

CRP = C-reactive protein; DAS28 = Disease Activity Score-28; HAQ-DI = Health Assessment Questionnaire – Disability Index; PASI = Psoriasis Area and Severity Index; hs-CRP = high-sensitivity C-reactive protein; PGA = Physician's Global Assessment; PsA = psoriatic arthritis; PsO = plaque psoriasis; SJC = swollen joint count; sPGA = static Physician's Global Assessment; TJC = tender joint count, V = visit; VAS = visual analog scale.

^a Assessments are derived by calculations using PsA assessments and hs-CRP assay.

8.1.1. Efficacy Assessments

8.1.1.1. Psoriasis Area and Severity Index (PASI 75, PASI 90, PASI 100)

The PASI will be used to assess PsO and PsA. The PASI combines assessments of the extent of body-surface involvement in 4 anatomical regions (head, trunk, arms, and legs) and the severity of desquamation (scaling), erythema, and plaque induration/ infiltration (thickness) in each region, yielding an overall score from 0 for no psoriasis up to 72 for the most severe disease (Fredriksson and Pettersson 1978). The PASI has been the most frequently used endpoint and measure of psoriasis severity in clinical trials (EMA 2004; Menter et al. 2008). A clinically meaningful response is a PASI 75, which represents at least a 75% decrease (improvement) from the baseline PASI score. As minimum treatment response, the European and German guidelines mention a PASI 50 response. Higher levels of clearance (PASI 90), as well as complete resolution of psoriasis (PASI 100), have become additional endpoints because of the increasing recognition of the association of higher clearance with greater health-related quality of life (Puig 2015).

Participants achieving PASI 75, 90, or 100 are defined as having an improvement of at least 75%, 90%, or 100%, respectively, in the PASI, compared to baseline.

8.1.1.2. Static Physician Global Assessment

The sPGA is the physician's determination of the participant's psoriatic lesions, overall, at a given time point. The sPGA is recommended as an endpoint to assess efficacy in the treatment of PsO/PsA (EMA 2004). Overall, lesions are categorized by descriptions for induration, erythema, and scaling. For the analysis of responses, the participant's PsO/PsA is assessed as clear (0), minimal (1), mild (2), moderate (3), severe (4), or very severe (5).

8.1.1.3. Percentage of Body Surface Area

The investigator will evaluate the percentage involvement of PsO/PsA on each participant's BSA on a continuous scale from 0% (no involvement) to 100% (full involvement), in which 1% corresponds to the size of the participant's palm of the hand, including the palm, fingers, and thumb (NPF 2018).

8.1.2. American College of Rheumatology 20, 50, and 70 Responder Index

ACR20, ACR50, and ACR70 responses are efficacy measures which for which a participants must satisfy the following:

- 1) $\geq 20\%$, $\geq 50\%$, and $\geq 70\%$ improvement from baseline in tender joint count (TJC); and
- 2) $\geq 20\%$, $\geq 50\%$, and $\geq 70\%$ improvement from baseline in swollen joint count (SJC); and
- 3) $\geq 20\%$, $\geq 50\%$, and $\geq 70\%$ improvement from baseline in at least 3 of the following 5 ACR Core Set criteria:
 - a. Patient's Assessment of Pain Visual Analog Scale (VAS)
 - b. Patient Global Assessment of Disease Activity VAS
 - c. Physician Global Assessment of Disease Activity VAS
 - d. Patient's assessment of physical function as measured by the Health Assessment Questionnaire – Disability Index (HAQ-DI)

- e. Acute-phase reactant as measured by high-sensitivity C-reactive protein (hs-CRP) assay

ACR20, ACR50 and ACR70 responses will be assessed over Week 24 (Visit 6).

American College of Rheumatology Core Set

Tender Joint Count

For ACR measures, the number of tender and painful joints will be determined by examination of 68 joints (34 joints on each side of the participant's body). The 68 joints to be assessed and classified as tender or not tender are detailed in Section 10.7. Any joints that require intra-articular injections during the study (according to Section 6.8) should be excluded from evaluation from the time of the injection to the conclusion of the study.

Joints will be assessed for tenderness by pressure and joint manipulation on physical examination. The participant will be asked for pain sensations on these manipulations and watched for spontaneous pain reactions. Any positive response on pressure, movement, or both will then be translated into a single tender-versus-nontender dichotomy.

Joint assessments will be performed by an independent, blinded assessor to minimize bias. The same assessor should preferably perform the TJC and SJC for a given participant particularly during the Induction Dosing Period (Period 2) to minimize interobserver variation. The blinded joint assessor will not be involved in participant care and is asked not to discuss disease activity or treatment with participants or principal investigator.

Missing, replaced, ankylosed, or arthrodesed joints will be identified by the investigator at the Screening Visit and will be excluded from evaluation during the trial.

Swollen Joint Count

For ACR measures, the number of swollen joints will be determined by examination of 66 joints (33 joints on each side of the participant's body). The 66 joints to be assessed and classified as swollen or not swollen are detailed in Section 10.7. Any joints that require intra-articular injections during the study (according to Section 6.8) should be excluded from evaluation from the time of the injection to the conclusion of the study.

Joints will be classified as either swollen or not swollen. Swelling is defined as palpable fluctuating synovitis of the joint. Swelling secondary to osteoarthritis will be assessed as not swollen, unless there is unmistakable fluctuation. Dactylitis should be counted as 1 joint.

Missing, replaced, ankylosed, or arthrodesed joints will be identified by the Investigator at the Screening Visit and will be excluded from evaluation during the trial.

Joint assessments will be performed by an independent, blinded assessor to minimize bias. The same assessor should preferably perform the TJC and SJC for a given participant particularly during the Induction Dosing Period (Period 2) to minimize interobserver variation. The blinded joint assessor will not be involved in participant care and will be instructed not to discuss disease activity or treatment with participants or principal investigator.

Patient's Assessment of Pain Visual Analog Scale

Patient's Assessment of Pain VAS will be administered only to PsA participants. The question related to pain assessment will be included in HAQ-DI assessment.

The participant will be asked to assess his/her current level of joint pain by marking a vertical tick on a 100-mm horizontal VAS where the left end represents no joint pain and the right end represents worst possible joint pain. The Patient's Assessment of Pain VAS should be administered *prior to* the TJC and SJC examinations.

Results will be expressed in millimeters, measured between the left end of the scale and the crossing point of the vertical line of the tick; *this procedure is applicable for all VAS used in the trial.*

Patient's Global Assessment of Disease Activity Visual Analog Scale

The participant's overall assessment of his/her PsA activity will be recorded using the 100 mm horizontal VAS where the left end represents no disease activity, and the right end represents extreme disease activity.

Physician's Global Assessment of Disease Activity Visual Analog Scale

The Investigator will be asked to give an overall assessment of the severity of the participant's current PsA activity using a 100 mm horizontal VAS, where 0 represents no disease activity and 100 represents extremely active disease. The investigator making the assessment must be a rheumatologist or medically qualified physician. The same assessor should preferably perform the Physician's Global Assessment of Disease Activity VAS for a given participant particularly during the Induction Dosing Period (Period 2) to minimize interobserver variation.

Patient's Assessment of Physical Function as Assessed by the Health Assessment Questionnaire-Disability Index

The HAQ-DI is a patient-reported standardized questionnaire that is commonly used in PsA to measure disease-associated disability (assessment of physical function). It consists of 24 questions referring to 8 domains: dressing/grooming, arising, eating, walking, hygiene, reach, grip, and other daily activities (Fries et al. 1980; Fries et al. 1982).

The disability section of the questionnaire scores the participant's self-perception on the degree of difficulty (0 = without any difficulty, 1 = with some difficulty, 2 = with much difficulty, and 3 = unable to do), covering the 8 domains. The reported use of special aids or devices and/or the need for assistance of another person to perform these activities is also assessed. The scores for each of the functional domains will be averaged to calculate the functional disability index. Details of scoring and calculations are presented in the statistical analysis plan (SAP).

C-Reactive Protein

CRP will be the ACR Core Set measure of acute phase reactant. It will be measured with a high sensitivity assay at the central laboratory to help assess the effect of ixekizumab on the participant's PsA.

Disease Activity Score based on C-Reactive Protein

The DAS28-CRP is a measure of disease activity in 28 joints that consists of a composite numerical score utilizing the following variables: TJC, SJC, hs-CRP (measured in mg/L), and Patient's General Assessment recorded by participants on a 0 to 100 mm VAS.

For DAS28-CRP, the 28 joints to be examined and assessed as tender or not tender for TJC and as swollen or not swollen for SJC are a subset of those assessed for the TJC and SJC, and include 14 joints on each side of the participant's body: the 2 shoulders, the 2 elbows, the 2 wrists, the 10 metacarpophalangeal joints, the 2 interphalangeal joints of the thumb, the 8 proximal interphalangeal joints, and the 2 knees (Smolen et al. 1995). The following equation will be used to calculate the DAS28-CRP (Vander Cruyssen et al. 2005):

$$DAS28 - CRP = 0.56(\sqrt{TJC28}) + 0.28(\sqrt{SJC28}) + 0.36(\ln(CRP + 1)) + 0.014(VAS) + 0.96$$

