[47] Are currently receiving treatment with any biologic or small molecule therapy for PsA or PsO, including investigational therapies (such as, but not limited to, a TNFi, IL-1 receptor antagonists, IL-6 inhibitor, anti-IL-12/23p40, T cell or B cell targeted therapies, phosphodiesterase [PDE] 4 inhibitors, or Janus kinase [JAK] inhibitors), or have received denosumab.

[48] Have received treatment with IL-17 or IL12/23 targeted Mab therapy.

[49] Have used disease-modifying antirheumatic drug (DMARDs) other than MTX, leflunomide, sulfasalazine, or hydroxychloroquine (e.g., gold salts, cyclosporine, azathioprine, dapsone, 6-mercaptopurine, mycophenolate mofetil, or any other immunosuppressive agents) in the 8 weeks prior to baseline (Week 0, Visit 2).

Have discontinued MTX or sulfasalazine within the 8 weeks prior to baseline, or hydroxychloroquine within 12 weeks prior to baseline.

If taking MTX, leflunomide, sulfasalazine, or hydroxychloroquine must have been treated for at least 12 weeks prior to baseline and on a stable dose for at least 8 weeks prior to baseline, as follows: oral or parenteral MTX = 10 to 25 mg/week; leflunomide = 20 mg/day; sulfasalazine = up to 3 g/day; or hydroxychloroquine = up to 400 mg/day. The dose of these allowed concomitant medications must remain unchanged until W12 of the study, unless changes are required for safety issues. Local standard of care should be followed for concomitant administration of folic acid with MTX.

[50] Are receiving treatment with more than 1 conventional DMARD (MTX, leflunomide, sulfasalazine, or hydroxychloroquine) at study entry.
Note: Under no circumstances will simultaneous use of MTX and leflunomide be allowed at any time during the study for safety reasons.

[51] Have discontinued leflunomide within 4 weeks prior to baseline or have received leflunomide from 4 to 12 weeks prior to baseline (Week 0, Visit 2) and have not undergone a drug elimination procedure.

[52] Use of oral corticosteroids at average daily doses of >10 mg/day of prednisone or its equivalent, or use of variable doses of any oral corticosteroids, within 4 weeks prior to baseline (Week 0, Visit 2).

- [53] Have received any parenteral glucocorticoid administered by intraarticular, intramuscular, or intravenous (IV) injection within 6 weeks prior to baseline (Week 0, Visit 2), or for whom a parenteral injection of glucocorticosteroids is anticipated until W12 of the study.

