6.8. Concomitant Therapy

All concomitant medication taken during the study must be recorded on the Concomitant Medication CRF at the study visits indicated in the SoA (Section 1.3). Treatment with concomitant PsO and PsA therapies during the study will be permitted only as outlined in the inclusion and exclusion criteria (Sections 5.1 and 5.2, respectively) and as described in the paragraphs below. Participants taking permitted medications need to be documented to be in stable control. After trial enrollment, significant dose escalation of a concomitant medication should be discussed with Lilly medical before allowing participant to receive study intervention.

Table RHCZ.6.3 summarizes concomitant medications that are and are not permitted and their conditions for use during the study.

Table RHCZ.6.3. Concomitant Medications Permitted/Not Permitted in the Study and Conditions for Use

Drug Class	Permitted/Not Permitted during the Trial	Conditions for Use
Bath oils and oatmeal bath preparations	Permitted	Not to be used within 12 hours of a study visit.
NSAIDs, acetaminophen, or aspirin	Permitted	Allowed as needed.
Shampoos	Permitted	May not contain >3% salicylic acid, corticosteroids, coal tar, or vitamin D3 analogues. Not to be used within 12 hours of a study visit.
Topical moisturizers/emollients and other non-prescription topical products	Permitted	Do not contain urea, >3% salicylic acid, alpha- or beta-hydroxyl acids, corticosteroids, or vitamin D3 analogues. Not to be used within 12 hours of a study visit.
Topical steroids		
Mild (such as hydrocortisone)	Permitted	Permitted for use limited to the face, axilla, groin, and/or genitalia, as needed. These topical medications should not be used within approximately 24 hours before study visits requiring sPGA and PASI measures. More widespread use on large surfaces is not permitted.
Strong (such as mometasone), very strong (betamethasone) ^a , and halogenated steroids (clobetasone)	Not permitted	
Biologic agents other than study intervention as part of this protocol	Not Permitted	Washout periods before baseline (Week 0, Visit 2); at least 5 half-lives

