Abbreviations: CRS/CRP = clinical research scientist/clinical research physician; csDMARD = conventional synthetic disease-modifying antirheumatic drug; IL = interleukin; MTX = methotrexate; NSAID = nonsteroidal anti-inflammatory drug; PASI = Psoriasis Area and Severity Index; PsA = psoriatic arthritis; PsO = plaque psoriasis; PUVA = psoralen and ultraviolet A; RNA = ribonucleic acid; sPGA = static Physician Global Assessment; UVB = ultraviolet B.

^a Mason et al. 2002.

Additional drugs are to be avoided during the study unless required to treat an AE or for the treatment of an ongoing medical problem. If the need for concomitant medication arises, the investigator should base decisions on the participant and clinical factors. Any additional medication (including the limited use of therapeutic agents which, if used under treatment regimens other than for treating an AE or for appropriate medical management, might be considered PsO/PsA therapies) whether prescription or over-the-counter, used at baseline (Week 0, Visit 2) and/or during the course of the study, must be documented with the start and stop dates on the Concomitant Medications CRF.

Participants will maintain their usual medication regimen for other concomitant diseases throughout the study unless those medications are specifically excluded in the protocol.

Participants taking concomitant medications should be on stable doses at the time of baseline (Week 0, Visit 2) and should remain at a stable dose throughout the study, unless changes need to be made for an AE or for appropriate medical management. Other medications may be allowed if approved by the Sponsor or its designee.

Participants should be instructed to consult the investigator or other appropriate study personnel at the site before taking any new medications or supplements. Any changes in medications not addressed above should be discussed by the investigator with the Sponsor.

7. Discontinuation of Study Intervention and Participant Discontinuation/Withdrawal

Discontinuation of specific sites or of the study as a whole are handled as part of Section 10.1, Section 10.1.7.

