9.3.1 General Nonresponder Imputation for Clinical Response

Analysis of categorical efficacy and health outcomes variables will be assessed using a nonresponder imputation (NRI) method. Participants will be considered a nonresponder for the NRI analysis if they:

- do not meet the clinical response criteria (e.g., ACR20, PASI75, PASI90, PASI100, sPGA [0,1]);
- have missing clinical response data at a timepoint of interest (e.g., Week 12, Week 24);
- discontinue study treatment at any time prior to a timepoint of interest for any reason; or
- have no postbaseline observation.

The NRI may be applied at any time point specified for analysis.

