9.5 Statistical Analyses

9.5.1. General Considerations

Statistical analysis of this study will be the responsibility of Lilly.

Unless otherwise specified, continuous data will be summarized in terms of the mean, standard deviation, minimum, maximum, median, and number of observations. Categorical data will be summarized as frequency counts and percentages.

Baseline will be defined as the last non missing assessment recorded on or prior to the date of first injection for efficacy and health outcomes. In most cases, this will be the measure recorded at Week 0 (Visit 2). Change from baseline will be calculated as the visit value of interest minus the baseline value. For safety analyses using a baseline period, the baseline period is defined as the time from Visit 1 to the date/time of the first injection.

Any change to the data analysis methods described in the protocol will require an amendment ONLY if it changes a principal feature of the protocol. Any other change to the data analysis methods described in the protocol, and the justification for making the change, will be described in the clinical study report (CSR). Additional exploratory analyses of the data will be conducted, as deemed appropriate.

Complete details of the planned analyses will be documented in the SAP.

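### An injected joint leaves the count only after the injection and no nonresponder rule covers it, so one rescue injection can meet the joint part of Week 24 ACR20 in participants with few active joints

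*Protocol*

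**What the plan says.** Section 8.1.2 gives the rule under Tender Joint Count: "Any joints that require intra-articular injections during the study (according to Section 6.8) should be excluded from evaluation from the time of the injection". The exclusion lasts to the end of the study, and the rule is repeated under Swollen Joint Count. Joints that are missing, replaced, ankylosed or arthrodesed are handled differently: they "will be identified by the investigator at the Screening Visit and will be excluded from evaluation during the trial".

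ACR20 requires at least 20% improvement from baseline in both counts and in three of five other core items. Section 9.5.1 fixes the reference point: "Baseline will be defined as the last non missing assessment recorded on or prior to the date of first injection".

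Section 9.3.1 names ACR20 among the responses analysed with nonresponder imputation (NRI). It lists four triggers: criteria not met, missing response data, no postbaseline observation, and participants who "discontinue study treatment at any time prior to a timepoint of interest for any reason". An injection is not among them.

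Three places bear on whether the injection is allowed:
- Exclusion criterion [53] covers parenteral glucocorticoid, including intra-articular, within 6 weeks before baseline, and patients "for whom a parenteral injection of glucocorticosteroids is anticipated until W12 of the study".
- Section 6.8 opens with "Treatment with concomitant PsO and PsA therapies during the study will be permitted only as outlined in the inclusion and exclusion criteria" and as described in that section. Neither its text nor its table names intra-articular steroid.
- Section 7.2 provides for withdrawal when a participant needs a prohibited agent known to work in the indication.

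**The concern.** For joints unevaluable from Screening, the same joints are compared at baseline and follow-up. For an injected joint this need not be so. A joint active at baseline and injected later still sits in the baseline count but is gone from the follow-up count. The loss can then look like improvement, although the joint needed rescue treatment.

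ACR20 at Week 24 is the only PsA-specific secondary endpoint. Criterion [53] looks ahead only to Week 12, whereas criterion [61] excludes patients who will need joint surgery up to Week 24. The Schedule of Activities has joint counts at Week 12 and Week 24 and none between them. A joint that flares and is injected in that interval would therefore appear as active in no scheduled count.

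The permission question adds to this. If the injection is prohibited, Section 7.2 and the discontinuation trigger lead to nonresponse. If it is tolerated, the participant stays evaluable and can be a responder. Section 8.1.2 presumes the second by carrying its rule to the end of the study.

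**Working it through.** There is no figure in the plan to reproduce on this point. The check is how far one injection moves the two counts.

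**Inputs.** Entry needs at least 3 tender and 3 swollen joints (criterion [10]). The counts use 68 and 66 joints (Section 8.1.2). About 100 PsA participants are planned (Section 9.7).

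**Main case.** One joint, tender and swollen at baseline, is injected and excluded. All other joints are unchanged, and baseline stays as recorded at b active joints.

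- Raw improvement (follow-up count = remaining active joints) = 1/b.
- Prorated improvement = 1 − [(b − 1)/b] × [N/(N − 1)], with N = 68 or 66.

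| b | Raw | Prorated, TJC (N = 68) | Prorated, SJC (N = 66) |
|---|---|---|---|
| 3 | 33.3% | 32.3% | 32.3% |
| 4 | 25.0% | 23.9% | 23.8% |
| 5 | 20.0% (met) | 18.8% (not met) | 18.8% (not met) |
| 6 | 16.7% | 15.4% | 15.4% |

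Both counts must reach 20%, so the larger baseline count governs. The limit is 5 raw and 4 prorated. With the joint removed from baseline as well, improvement is 1 − (b − 1)/(b − 1) = 0%. A hip cannot produce this case, because its swelling is not scored.

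**A matched joint set is not a complete cure.** Take 5 active joints at baseline, 4 of them still active, and a further joint that was quiet at baseline, flared and was injected. Excluding it gives 1 − 4/5 = 20.0%, and a matched baseline is still 5, so again 20.0%. Counted as active, the result is 1 − 5/5 = 0%. An NRI trigger settles both cases.

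**Opposite direction.** Take 5 active at baseline, 4 still active, and an injected joint inactive at baseline. Raw improvement is 20.0%. Prorated, 4 × 68/67 = 4.06 and 1 − 4.06/5 = 18.8% (also 18.8% with 66/65), so a responder is lost.

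**Effect on the rate.** One participant in 100 is 1.0 percentage point. The number affected is not given. Over an assumed range of 1 to 10, the rate moves 1 to 10 points. For comparison, the 95% CI half-width at an assumed 50% rate is 1.96 × √(0.5 × 0.5/100) = 9.8 points.

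**Exploratory DAS28-CRP.** If the joint is among the 28 and both 28-joint counts equal b, the score falls by (0.56 + 0.28) × (√b − √(b − 1)): 0.27, 0.23 and 0.20 at b = 3, 4 and 5.

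**The case against.** The strongest reply is that the protocol never says how the count is derived once a joint is excluded. Section 8.1.2 tells assessors not to evaluate the joint. Section 9.5.1 says which assessment is baseline, not which joints enter the comparison. The form in Appendix 7 separates absent (0) from not applicable (9), which argues against scoring an excluded joint as inactive, although its footnote assigns code 9 only to replaced, ankylosed or arthrodesed joints. If an unevaluable joint made the count missing, Section 9.3.1 would already give nonresponse. Sections 9.5.1 and 9.5.3 leave analysis detail to the SAP, which could prorate or add a rule.

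Much of this stands. A reader might infer that the protocol fixes a raw count against an unadjusted baseline. It does not: that is one reading of its silence, and proration is another. What the reply leaves open is that the protocol itself states the exclusion and the NRI list, that proration only lowers the limit from 5 to 4, and that whether a treatment is allowed is for the protocol to settle.

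The second reply is that the injection is already prohibited, since Section 6.8 permits only what is outlined, and withdrawal then leads to NRI. That reading is possible. Section 6.8 also mentions "limited use of therapeutic agents which, if used under treatment regimens other than for treating an AE or for appropriate medical management", but in a sentence about recording medication, so it is weak evidence of permission. Against prohibition, Section 8.1.2 expects evaluation to continue after an injection and cites Section 6.8 for it. The text supports neither reading clearly.

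Third, the case is narrow: an injection before Week 24, no discontinuation, low counts, too little improvement elsewhere, and still three of five other core items improved. This stands and limits the weight of the point.

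**Conclusion.** The point holds as a minor one. The exclusion starts at the injection, nothing removes the joint from baseline, and no NRI trigger covers it. If the count is the remaining active joints, one injection can meet the joint part of ACR20 at baseline counts up to 5, or up to 4 if prorated. This assumes the joint was tender and swollen at baseline and the others are unchanged. The unclear status of intra-articular steroid means that the same participant could be classified either way.

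Two stronger conclusions might be inferred and are not supported. One is that the injection alone makes an ACR20 responder: it supplies only the joint part. The other is that the reported rate will be materially inflated. The number of injected participants is unknown and probably small, and the direction can reverse under proration or if the count is treated as missing. ACR20 is a secondary endpoint reported with a confidence interval and no hypothesis test, so only the described rate is affected, by about 1 percentage point per participant at 100.

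**What to change.** 1. Add to the nonresponder list in Section 9.3.1, for ACR endpoints: *have an intra-articular glucocorticoid injection for PsA before the timepoint of interest*. This settles ACR20 under any joint-count convention.
2. State in Section 6.8 whether and when intra-articular steroid is allowed during the study, and that prohibited use leads to discontinuation and hence to NRI.
3. Optionally, for the exploratory DAS28-CRP and component counts only, carry forward the joint's last pre-injection status or use the same joint set at baseline and follow-up. Scoring every injected joint as tender and swollen is not advised: it would record as swollen a joint that never was, and it adds nothing for ACR20 once item 1 is in place.

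The cost is two or three sentences in an amendment and a record of the joint and reason for each injection; Section 6.8 already requires start and stop dates for additional medication. No visits or assessments are added. The downside is a slightly lower reported ACR20 rate, about 1 percentage point for each participant reclassified as a nonresponder.
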